6.2 Safety Variables

Safety will be assessed by evaluation of the following variables:

- Treatment-emergent AEs (TEAEs; frequency, severity, seriousness, and relationship to study drug).
- Clinical laboratory variables (hematology, biochemistry, PSA and testosterone)
- Vital signs (systolic and diastolic blood pressure and pulse rate) and weight
- 12-lead ECG

Treatment-Emergent Adverse Event (TEAE)

A TEAE is defined as an AE that occurs or worsens at any time during the treatment emergent period. The treatment emergent period for double-blind treatment period is defined as the time interval from the first study drug intake up to 30 days after the date of the last dose of study drug, study discontinuation, the start of new antineoplastic therapy or prior to first open-label treatment, whichever occurs first. The treatment emergent period for open-label phase is defined as the time interval from the first open-label study drug intake up to 30 days after the date of the last dose of study drug, study discontinuation or the start of new antineoplastic therapy, whichever occurs first.

If AE start date is the same date as the study start, then it will be considered as a TEAE if the box '*Onset after first dose of study drug taken*' is ticked in the Electronic case report form(eCRF). If a patient experiences an event both during the pre-investigational period and during the investigational period, the event will be considered as TEAE only if it has worsened in severity (i.e. it is reported with a new start date and an increased NCI-CTCAE grade).

AE with both a missing start and stop dates, and AEs with a missing start date but has a known stop date which is on or after the first dose of study drug will be considered treatment-emergent.

AEs will be coded to SOC and preferred term using MedDRA v23.0 (or later version) and severity graded using National Cancer Institute's Common Terminology Criteria version 4.03 (NCI-CTCAE v4.03) for AEs.

Drug-Related TEAE

A drug related TEAE is defined as any TEAE with a causal relationship to study drug as assessed by the investigator in the eCRF (by answering 'YES') or with missing assessment of the causal relationship.

AEs of Special Interest

AEs of special interest are defined in Table 7

Table 7 Selection Criteria for AEs of Special Interest

Event of special interest	Selection based on MedDRA 23.0
Convulsion	Narrow SMQ of 'Convulsions'
Hypertension	Narrow SMQ 'Hypertension'

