- TEAEs, excluding serious AEs, that equal to or exceed a threshold of 5.0% in any treatment group,
- TEAEs leading to death,
- drug related TEAEs leading to death,

The number and percentage of patients with TEAEs, classified by preferred terms by decreasing frequency within the overall group will also be summarized.

The number and percentage of patients with TEAEs that equal to or exceed a threshold of 5.0% in any treatment group, classified by preferred terms by decreasing frequency within the overall group, on a 6 monthly basis (0- <3 months; 3- <6 months; 6- <12 months; 12 months or more). The percentage of patients are calculated based on the number of patients still on treatment at the time point corresponding to the lower limit of the time intervals.

To adjust for the treatment duration, the number of TEAEs per 100 patients-years will be summarized, as classified by SOC and PT, per treatment group and overall. The number of TEAEs per 100 patients-years is calculated as the number of events *100 / (sum of the

treatment emergent period duration of all patients treated in the corresponding treatment group, in years).

The number and percentage of patients with TEAEs, as classified by SOC and preferred terms will also be summarized by maximum severity (reported according to NCI- CTCAE version 4.03).

In the patient count, if a patient has multiple TEAEs with the same SOC or PT, but with different severity, then the patient will be counted only once with the worst severity. However, if any of the severity values are missing then the patient will be counted only once with missing severity. In the AE count, the AEs will be presented in each category they were classified to. An AE can be reported multiple times in the AE module if its toxicity grade changes. Summaries will be provided for:

- TEAEs by NCI- CTCAE
- drug related TEAEs by NCI- CTCAE,
- serious TEAEs by NCI- CTCAE

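### SAP 7.5.1: the open-ended last row of the adverse-event interval table mixes risk with time on treatment, and the event counted in the patient-year rate is not defined

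*SAP*

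**What the plan says.** SAP 7.5.1 describes two separate tables.

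- **Interval table.** It gives the number and percentage of patients with TEAEs reaching 5% in either arm. The text calls it six-monthly and then lists 0 to <3, 3 to <6, 6 to <12, and 12 months or more. On the denominator it says: "The percentage of patients are calculated based on the number of patients still on treatment at the time point corresponding to the lower limit" of each interval. SAP 6.2 runs the treatment-emergent period "up to 30 days after the date of the last dose of study drug", or to an earlier study discontinuation, new antineoplastic therapy or open-label start.
- **Rate table.** Introduced as an adjustment for treatment duration: "The number of TEAEs per 100 patients-years is calculated as the number of events" times 100, divided by the summed "treatment emergent period duration of all patients treated in the corresponding treatment group, in years". It has no time intervals.

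A later paragraph, on tables by maximum severity, counts each patient once at the worst grade. For events it says: "In the AE count, the AEs will be presented in each category they were classified to". It then adds: "An AE can be reported multiple times in the AE module if its toxicity grade changes". SAP 6.2, on events that span the pre-investigational and investigational periods, describes a worsened event this way: "it is reported with a new start date and an increased NCI-CTCAE grade". No rule says how such records are combined when events, rather than patients, are counted. The overview table in SAP 7.5.1 has 12 lines that count TEAEs.

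**The concern.** A reader of the interval table will compare the arms row by row. The first three rows have fixed widths, so patients in both arms are watched for similar lengths of time. The last row has none: each patient counts from month 12 until the treatment-emergent period ends. If one arm stays on treatment longer, its patients have more time to record an event in that row, and the percentage rises at the same hazard. The numerator and denominator also differ. A patient who stopped just before a lower limit, but is still within 30 days of the last dose, can add an event without being in the denominator.

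In the rate table the denominator matches the TEAE period. The gap is in the numerator: two programmers could follow the SAP and produce different event counts, one by records and one by episodes. For an event that persists, the chance of a further grade record grows with exposure, so this could work against the table's purpose. Protocol 1.3 shows how the sponsor reads this metric. It interprets earlier studies by rates per 100 patient-years, some of them very close (headache 6.9 versus 7.0).

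**Working it through.** The documents give no adverse-event rate for this trial, so there is no planned figure to reproduce. The check asks what each table shows when the true hazard is the same in both arms.

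**Inputs**
- Hazard λ = 10 per 100 patient-years = 10/1200 = 0.00833 per month in both arms (assumed).
- Median time on treatment of 17.9 and 7.1 months: the exposure medians of the earlier combined phase 3 studies in Protocol 1.3, used here as an assumption, with exponential durations. Then μ = ln 2/17.9 = 0.0387 and ln 2/7.1 = 0.0976 per month.
- Follow-up of 12 to 27 months: 15 months of recruitment plus 12 of follow-up (Protocol synopsis, sample size). An assumed longer case is 24 to 39 months.

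**Open-ended row, by hand, without the 30-day tail.** With k = λ + μ, and follow-up beyond month 12 uniform from a to b, the chance of at least one event is

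(λ/k) × [1 − (e^(−ka) − e^(−kb)) / (k(b − a))]

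- k = 0.0471 and 0.1060; λ/k = 0.177 and 0.0786.
- Planned follow-up (a = 0, b = 15): 0.177 × 0.283 = 5.0% versus 0.0786 × 0.499 = 3.9%.
- Longer follow-up (a = 12, b = 27): 0.177 × 0.592 = 10.5% versus 0.0786 × 0.860 = 6.8%.

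**With the 30-day tail**, by simulation of 1,000,000 patients per arm (enzalutamide versus placebo):

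| Row | 12–27 months of follow-up | 24–39 months of follow-up |
|---|---|---|
| 0 to <3 | 2.4% vs 2.3% | 2.4% vs 2.3% |
| 3 to <6 | 2.4% vs 2.4% | 2.4% vs 2.4% |
| 6 to <12 | 4.5% vs 4.1% | 4.5% vs 4.1% |
| 12 or more | 5.2% vs 4.3% | 10.9% vs 7.4% |
| closed at 12 to <18 | 3.7% vs 3.3% | 4.5% vs 4.1% |
| per 100 patient-years, 12 or more | 10.0 vs 10.0 | 10.0 vs 10.0 |

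With medians of 18 and 9 months (the planning medians for time to PSA progression, used only as a proxy), the open-ended row gives 5.2% versus 4.6% and 10.9% versus 8.4%.

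**Numerator-only patients.** Without a follow-up limit, patients who stopped before a lower limit but are still in the 30-day tail equal about 3.9% of the denominator in the longer-exposed arm and 10.1% in the other. With about half a month of tail left, they add 0.039 × 0.5 × 0.83% = 0.02 and 0.101 × 0.5 × 0.83% = 0.04 percentage points. This is small and runs against the open-row effect.

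**Event counting in the rate table**
- One event per episode: 10.0 versus 10.0 per 100 patient-years, so no bias.
- Equal records per event, 1.3 in both arms: 13 versus 13, ratio 1.00.
- Unequal records, 1.3 versus 1.1: 13/11 = 1.18. Reversed: 11/13 = 0.85.
- Events that never resolve, with g further grade records per month: an event starting at time s adds g(T − s) records on average, where T is the length of the treatment-emergent period. The record rate is therefore λ × [1 + g × E(T²)/(2E(T))]. At planned follow-up, g = 0.01 gives 10.9 versus 10.7 (ratio 1.02) and g = 0.05 gives 14.4 versus 13.4 (ratio 1.07). With 24 to 39 months of follow-up the range is 1.04 to 1.14. The values of g are assumed.

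**The case against.** Much can be said for the plan. The tables are descriptive and no safety test is specified. The overview pairs event counts with patient counts and percentages, the severity tables count each patient once, and all AEs are listed. The explicit intervals make the six-monthly label a slip rather than an ambiguity. At planned follow-up the last-row gap is under one percentage point. All of this stands and sets the weight of the point.

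A reader might also go further than the text allows, in four ways.

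- **That the exposure-adjusted table uses faulty intervals.** It has none, and its denominator covers the same period as its numerator. The stated aim of adjusting for treatment duration belongs to that table only.
- **That the SAP counts every grade change as a new event.** The sentence on multiple records sits in the severity paragraph and explains why an event may appear under several grades. For the rate, the counting unit is left open; no wrong rule is stated.
- **That the rates must therefore differ between arms.** A records-per-event factor common to both arms cancels in the ratio. A factor such as 1.25/1.10 = 1.14 needs unequal re-grading, for which the documents give no figure.
- **That the last row could show something like 34% versus 21% at equal risk.** That follows from 0.02/(0.02 + ln 2/18) and 0.02/(0.02 + ln 2/9). It needs unlimited follow-up, a hazard of 2% per month and PSA-progression medians standing in for treatment duration, although treatment continues to radiographic progression.

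**Conclusion.** The point holds as two modest weaknesses in descriptive safety tables.

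The open-ended row is a stated rule that gives a misleading comparison when followed. Its size depends on follow-up: about 0.9 percentage points (5.2% versus 4.3%) at 12 to 27 months and 3.5 points (10.9% versus 7.4%) at 24 to 39 months. Both assume equal hazards of 10 per 100 patient-years, exponential time on treatment and the earlier studies' exposure medians. Longer follow-up is plausible: the planned study start is 3Q2019, the SAP is dated December 2022, and SAP 7.3.1 tabulates exposure up to year 4. The 30-day mismatch is real but negligible in size.

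The undefined event is an omission. If records were counted, the rates would be too high in both arms. The ratio would move only if records per event differ by arm: 1.02 to 1.07 for persistent events at planned follow-up, under assumed re-grading of 0.01 to 0.05 per month. If episodes are counted, there is no bias at constant hazard.

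Neither weakness touches the primary analysis.

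**What to change.** In SAP 7.5.1:

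1. **Interval table.** Correct the six-monthly label. Replace the open row with closed intervals, for example 12 to <24 and 24 to <36 months. Use patients still in the treatment-emergent period at the interval start for both numerator and denominator. Add events per 100 patient-years within each interval. This last step matters most: closing the row narrows the gap (4.5% versus 4.1% for 12 to <18 months at longer follow-up), while patient-time removes it.
2. **Event counts and rates.** State that one event is one AE episode. Collapse consecutive grade-change records of the same preferred term in a patient into one event at its worst grade, and fix the gap allowed between records. Apply this to the rate table and to the overview lines that count TEAEs.

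The cost is SAP wording and minor programming; SAP section 1 allows revision before database hard lock. The interval table gains rows, and late ones will be thin. With 60 placebo patients and a 7.1-month median, about 60 × 2^(−12/7.1) = 19 would start the 12-month row and 60 × 2^(−24/7.1) = 6 the 24-month row, if follow-up reaches that far. Patient numbers and patient-years should be printed beside each rate.

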7.5.2 Clinical Laboratory Evaluation

Laboratory assessment will be done for the following parameters as applicable:

Hematology	Biochemistry	Other*
Red blood cell count	Albumin	Testosterone
White blood cell count	Alkaline phosphatase (ALP)	PSA**
White blood cell differential	Alanine aminotransferase (ALT)	
Hemoglobin	Aspartate aminotransferase (AST)	
Hematocrit	Blood urea nitrogen	
Platelet count	Blood urea	
	Calcium	
	Creatinine	
	Glucose	
	Phosphorus	
	Potassium	
	Sodium	
	Total bilirubin	
	Total protein	

*Testosterone and PSA will not be assessed for open-label phase.

**PSA may be taken locally for assessments affected by COVID-19.

Quantitative clinical laboratory variables (hematology, serum chemistry and testosterone), will be summarized using mean, standard deviation, minimum, maximum and median for each treatment group at each visit. Additionally, a within-patient change will be calculated as the post-baseline measurement minus the baseline measurement and summarized in the same way.

Based on the NCI-CTCAE grade of laboratory data, clinical laboratory evaluations will be summarized by grade and by visit as applicable, for their comparison to the upper limit. Shift analysis tables on the enzalutamide group will present the shift from baseline to each visit and to the highest grade among the post-baseline visits, by grade. The number and percentage of patients with an increase in grade will be summarized by visit.

Each laboratory result will also be classified as low (L), normal (N), or high (H) at each visit according to the laboratory supplied reference ranges.

Laboratory data will be displayed in listings. PSA results from local laboratory will be flagged in the listings.

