## Treatment-emergent Adverse Events

Overall, enzalutamide treatment was generally well tolerated across the combined phase 3 studies. Overall, treatment-emergent adverse events (TEAEs) were experienced by 95.1% of patients in the enzalutamide group and 90.1% of patients in the placebo group of the combined phase 3 studies. When TEAEs occurring in at least 5% of patients in the enzalutamide group and with a  $\geq 2\%$  higher incidence than the placebo group were adjusted for treatment duration, the differences between the enzalutamide group and the placebo group were reduced (event rate per 100 patient-years of treatment): hypertension (8.1 enzalutamide vs 5.4 placebo), and fall (8.8 vs 4.7). When adjusted for treatment duration, the other frequently reported TEAEs with a  $\geq 2\%$  higher incidence in the enzalutamide group than the placebo group had event rates per 100 patient-years of treatment that were either lower in the enzalutamide group than the placebo group or had an equal event rate: fatigue (21.5 enzalutamide vs 25.3 placebo), back pain (14.6 vs 22.6), nausea (13.8 vs 23.8), arthralgia (13.1 vs 18.9), constipation (11.4 vs 17.6), decreased appetite (11.2 vs 16.0), hot flush (10.9 vs 13.3), diarrhea (10.5 vs 15.2), asthenia (8.8 vs 10.6), headache (6.9 vs 7.0), hematuria (6.7 vs 8.0), musculoskeletal pain (6.6 vs 8.3), edema peripheral (6.4 vs 10.0), weight decreased (6.2 vs 7.3), dizziness (5.9 vs 6.8), nasopharyngitis (4.4 vs 5.7) and insomnia (4.3 vs 5.3).

The pooled phase 3 safety data confirms that convulsion/seizure, cognitive and memory impairment, fatigue related events, neutropenia/neutrophil count decreased, fall, fracture and hypertension are adverse events of special interest (AESI) for enzalutamide. Posterior reversible encephalopathy syndrome (PRES) is also considered an AESI for enzalutamide; however, this is based on cases reported during postapproval use of enzalutamide and not on events occurring in clinical studies.

Severe cutaneous adverse reactions, including acute generalized exanthematous pustulosis, dermatitis bullous, dermatitis exfoliative generalized, drug reaction with eosinophilia and systemic symptoms, erythema multiforme, exfoliative rash, Stevens-Johnson syndrome, toxic epidermal necrolysis and toxic skin eruption have been reported in post-marketing cases.

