### **7.5.2 Laboratory Assessments**

Clinical laboratory evaluations (including hematology and serum chemistry) will be presented for each visit using descriptive statistics (n, mean, SD, median, minimum and maximum values). Change from baseline will also be presented. Shift analysis tables will present the shift from baseline for using NCI-CTCAE grade and lab reference range indicator. All clinically significant abnormal laboratory values will be recorded as AEs and graded using NCI-CTCAE guidelines. A listing of subject laboratory values will be provided.

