Neutrophil count decreased	Preferred terms of 'Neutrophil count decreased', 'Neutropenia', 'Agranulocytosis', 'Granulocyte count decreased', 'Granulocytopenia', 'Febrile neutropenia', 'Neutrophil percentage decreased', 'Band neutrophil count decreased', 'Band neutrophil percentage decreased', 'Neutropenic sepsis', 'Neutropenic infection' and 'Neutrophil count abnormal'
Cognitive/memory impairment	All preferred terms under the MedDRA High Level Group Term: 'Mental impairment disorders'
Ischemic Heart Disease	Narrow SMQs of 'Myocardial Infarction' and 'Other Ischaemic Heart Disease'
Other selected cardiovascular events	Narrow SMQs of 'Haemorrhagic central nervous system vascular conditions', 'Ischaemic central nervous system vascular conditions' and 'Cardiac failure'
Posterior reversible encephalopathy syndrome	Preferred term 'Posterior reversible encephalopathy syndrome'
Fatigue	Preferred terms of 'Fatigue', 'Asthenia'
Fall	Preferred term 'Fall'
Fractures	All preferred terms under the MedDRA High Level Group Terms: 'Fractures' and 'Bone and joint injuries'
Loss of consciousness	Preferred terms of 'Loss of consciousness', 'Syncope', 'Presyncope'
Thrombocytopenia	Preferred terms of 'Thrombocytopenia', 'Platelet count decreased'
Musculoskeletal events	Preferred terms of 'Back pain', 'Arthralgia', 'Myalgia', 'Musculoskeletal pain', 'Pain in extremity', 'Musculoskeletal stiffness', 'Muscular weakness', 'Muscle spasms'
Severe cutaneous adverse reactions (SCAR)	Narrow SMQ of 'Severe cutaneous adverse reactions'
Angioedema	Narrow SMQ of 'Angioedema'
Rash	All preferred terms including term 'Rash'

Event of special interest	Selection based on MedDRA 23.0

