7 STATISTICAL METHODOLOGY

7.1 General Considerations

For continuous variables, descriptive statistics will include the number of patients (n), mean, standard deviation, median, minimum and maximum. When needed, the use of other percentiles (e.g.10%, 25%, 75% and 90%) will be mentioned in the relevant section.

Frequencies and percentages will be displayed for categorical data. Unless otherwise specified, percentages by categories will be based on the number of patients with no missing data, i.e. will add up to 100%.

All summary tables and figures will be presented by treatment arm and overall for double-blind treatment period, unless stated otherwise. For open-label phase, only selected summaries will be presented , the titles of selected tables, listings and figures for open-label phase summaries will be written out to indicate the “Open-label Phase”, refer to Appendix 3 for detailed analyses for open-label phase. All listings will be produced by site and patient id numbers in ascending order.

Disposition, demographics and other baseline characteristics as well as efficacy data will summarized based on the ITT population, unless stated otherwise. Safety analysis summary and other summaries based on SAF are presented by actual treatment received, unless stated otherwise.

All statistical comparisons will be made using two sided tests comparing double-blind enzalutamide to double-blind placebo. All null hypotheses will be of no treatment difference. All analyses will be based on IRT captured strata. Multiplicity adjustment was incorporated within the interim and final analysis of the primary endpoint according to the O’Brien-Fleming method with a Lan-DeMets alpha spending function (refer to Section 6.1.1.1). And no adjustment for multiplicity will be made for this study on the other endpoints, hence any p-values displayed for those endpoints are intended to be read descriptively.

All data processing, summarization, and analyses will be performed using SAS® Version 9.1.3 or higher. Specifications for table, figures, and data listing formats can be found in the TLF specifications for this study.

For the definition of subgroups of interest, please refer to Section 7.9.

A data analysis cut-off date for the database will be used. All data from visits or assessments done prior to the cut-off date will be reported.

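### SAP 7.5.2 specifies no two-arm table of the CTCAE grade reached for low laboratory values: the by-visit grade summary looks to the upper limit, and the shift tables cover enzalutamide alone

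*SAP*

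**What the plan says.** SAP 7.5.2 (Clinical Laboratory Evaluation) lays out the laboratory tables in this order:

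- Haematology, chemistry and testosterone get descriptive statistics and change from baseline, for each treatment group at each visit.
- The table of grades at each visit is worded this way: "clinical laboratory evaluations will be summarized by grade and by visit as applicable, for their comparison to the upper limit".
- For movement between grades, the plan is limited to one arm: "Shift analysis tables on the enzalutamide group will present the shift from baseline to each visit and to the highest grade". The last item is the worst grade seen after baseline.
- For worsening, a simple count is planned: "The number and percentage of patients with an increase in grade will be summarized by visit".
- Reference ranges supply a separate, ungraded description: "Each laboratory result will also be classified as low (L), normal (N), or high (H) at each visit".

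The SAP 7.1 default, which gives way to any specific statement elsewhere, is that "All summary tables and figures will be presented by treatment arm and overall for double-blind treatment period".

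Protocol 7.5 plans a tabulation of each subject's worst grade for a selection of adverse events and laboratory analytes. Protocol 7.5.2 adds: "Shift analysis tables will present the shift from baseline for using NCI-CTCAE grade and lab reference range indicator". Neither section names a direction or restricts the output to one arm.

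On the events concerned, Protocol 1.3 says that "neutropenia/neutrophil count decreased, fall, fracture and hypertension are adverse events of special interest (AESI) for enzalutamide". SAP Table 7 lists decreased neutrophil count and also thrombocytopenia among the events of special interest.

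**The concern.** Neutrophils, platelets and haemoglobin are of concern mainly when low. The protocol's own entry limits for them (exclusion criterion 11) are lower limits. A grade summary framed as a comparison with the upper limit looks the wrong way for these analytes.

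The shift tables could fill the gap, but they are written for one arm. Without a placebo table beside them, a fall in counts on enzalutamide cannot be separated from the background of metastatic disease, ADT and, in some subjects, recent docetaxel. The safety objective is a comparison of the two arms. At stake is whether a laboratory signal in two named safety events can be read by grade and by arm from the planned tables.

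**Working it through.** No arithmetic applies. The check is whether any planned output meets three conditions together: it covers the low direction, it covers both arms, and it shows the grade reached as measured in the laboratory.

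| Output | Direction | Arms | Grade reached, from laboratory data? |
|---|---|---|---|
| By-grade, by-visit summary (SAP 7.5.2) | Upper limit | Both, by the 7.1 default | Yes |
| CTCAE shift tables (SAP 7.5.2) | None stated | Enzalutamide only | Yes, each visit and worst |
| Increase in grade by visit (SAP 7.5.2) | None stated | Both, by default | No, only that the grade rose |
| Low, normal, high (SAP 7.5.2) | Both | No summary table stated | No grade |
| Descriptive statistics (SAP 7.5.2) | Minimum and maximum shown | Both | No grade |
| TEAEs by maximum grade, and grade 3 or higher (SAP 7.5.1) | Follows the reported term | Both | Grade shown, but only for reported events |

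Row by row:

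1. The by-visit summary fails on direction.
2. The shift tables fail on arms. The 7.1 default does not rescue them, because it yields where the SAP states otherwise, and here it does.
3. The increase-in-grade count fails on grade reached. A move from grade 0 to 1 counts the same as a move from 2 to 4. The sentence also follows closely on the upper-limit phrase, so a programmer could carry that limit over.
4. Classification and descriptive statistics carry no grade.
5. The adverse event tables depend on reporting. Under Protocol 5.5.1 an abnormal test is an adverse event only if it causes signs or symptoms, needs active intervention, leads to interruption or discontinuation of study medication, or is judged clinically significant. Under Protocol 5.5.1.1 a clinically significant finding linked to the underlying disease need not be reported unless it is worse than expected for that subject. Low counts attributed to metastatic disease can therefore be missing. The overview of events of special interest in SAP 7.5.1 gives patient counts without grades.

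No row meets all three conditions.

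Against the protocol, the SAP differs in three ways. The grade shift loses the placebo arm. The shift by reference range indicator is not carried over as a shift table. The worst post-baseline laboratory grade appears only inside the enzalutamide-only shift. By contrast, SAP 7.5.2.1 gives raised liver tests a dedicated threshold table by treatment group and overall.

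**The case against.** A reader might infer that laboratory grades are summarised only against the upper limit, or that low-direction toxicity is not graded anywhere. The documents do not support this. The shift and increase-in-grade sentences carry no stated direction, and the second falls under the by-arm default. Haematology is described by arm and visit, including the minimum and the change from baseline, so a marked between-arm difference in neutrophils or platelets could still show there.

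The events of special interest are also defined by adverse event terms: the neutrophil row of Table 7 begins "Preferred terms of 'Neutrophil count decreased', 'Neutropenia', 'Agranulocytosis". Reported events are tabulated by preferred term and maximum grade whatever the laboratory sentence says.

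A reader might also try to size the gap as the whole haematology panel, plus half of the gradings of analytes such as calcium and potassium. That ignores the tables above and rests on CTCAE content that the documents do not reproduce.

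Finally, the disputed sentence says *as applicable* and may be meant only for analytes graded against an upper limit. The SAP presents itself as an elaboration of the protocol, so it need not be read as cancelling the protocol's tables. The table layouts sit in separate specifications that were not available.

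Much of this stands: coverage is partial rather than absent, and the upper-limit phrase is ambiguous. Two things are not answered. The restriction of the shift tables to enzalutamide is explicit. And even on the generous reading, no sentence in the SAP calls for the low-direction grade in both arms.

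**Conclusion.** The point holds as a gap between the SAP and the protocol. Followed as written, the SAP specifies no two-arm table of the laboratory grade reached for low neutrophils, platelets or haemoglobin. It also narrows the protocol's shift tables to one arm. The remaining outputs give partial coverage, so this is not a loss of all graded low-direction information.

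The effect is confined to descriptive safety reporting. The primary endpoint and its error control are unaffected, and no number of patients can be derived from the documents. The conclusion assumes that CTCAE v4.03 grades these three analytes in the low direction, and that the unseen table specifications do not already supply the missing tables. If they do, the SAP text still needs to be brought into line with them.

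**What to change.** Three edits to SAP 7.5.2:

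1. Replace the upper-limit phrase with: *by CTCAE v4.03 grade, separately for the low and the high direction wherever CTCAE grades both, by visit and for the worst post-baseline value, for each treatment group*.
2. In the shift-table sentence, replace the restriction to enzalutamide with *for each treatment group*. Changing the upper-limit phrase alone would leave the one-arm shift standing.
3. Add the shift by reference range indicator planned in Protocol 7.5.2.

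The cost is SAP wording and a few more table pages from data already collected. SAP section 1 allows version-controlled revisions before database hard lock. No new assessments are needed.
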